8.2.3.3 Sensitivity Analysis #3

The third sensitivity analysis will be performed based on the subgroup of the RS who received all 6 (sc) doses of IMP in the treatment period, using the hypothetical & treatment policy strategy and same missing data handling method as mentioned in [Section 4.2.1](#).

The same stage-wise analysis approach as primary analysis ([Section 8.2.2](#)) will be repeated.

8.2.3.4 Sensitivity Analysis #4

The fourth sensitivity analysis will be performed for the primary endpoint on the FAS excluding confirmed COVID-19 cases under the treatment policy strategy.

The method to handle missing MG-ADL scores (including missing data after the intercurrent events) is specified in [Section 4.2.1](#).

The same stage-wise analysis approach as primary analysis ([Section 8.2.2](#)) will be repeated.

8.2.4 Supplementary analyses of the primary efficacy endpoint

8.2.4.1 Supplementary Analysis #1

The first supplementary analysis will be performed based on the RS, using the composite strategy (see details in [Section 8.1](#)). A trimmed mean approach, where missing data are assumed to be missing not at random (MNAR), will be used to impute missing MG-ADL scores (including the intercurrent events) with the worst score of the MG-ADL questionnaire.

The trimmed mean approach will be applied for each stage separately as follows:

1. Perform an analysis using ANCOVA model with treatment group, Baseline MG-ADL score, region, stratification factors (MuSK+/- and AChR+/-) as fixed effects excluding any study participants with missing data at Day 43 or who experienced an intercurrent event by Day 43.
2. Retain the coefficients from the model for Baseline MG-ADL score, region, and stratification factors (MuSK+/- and AChR+/-).
3. Calculate the adjusted endpoint for each study participant as based on the raw CfB and coefficients calculated from the ANCOVA in Step 1: $\text{Adjusted CfB} = \text{Raw CfB} - \text{Stratification Coefficient} * \text{Stratification (AChR/ MuSK)} - \text{Baseline Score Coefficient} * \text{Baseline MG-ADL score} - \text{Region Coefficient} * \text{Region}$.
4. Identify any study participants with missing data at Day 43 and any study participants who experienced any intercurrent event by Day 43. A worst score (i.e., 24) will be imputed for these study participants at Day 43 in order to flag them as worse responders than any subject who completes.
5. Determine the trim fraction to be used. This will be the maximum of dropout and intercurrent event rate in each of the three treatment groups. For example, if the rate of dropout/IE in the three groups is 10, 15 and 20% then the worst 20% of each group will be the trimmed.
6. Sort each treatment group in ascending order by adjusted endpoint Day 43 MG-ADL score and trim equal fractions from each treatment group that was calculated in Step 5 from the bottom.

7. Calculate the mean adjusted CfB score of the trimmed sample for each treatment group and the difference between trimmed means of each rozanolixizumab group and placebo.
8. Repeat Steps 5-7 (above) 10,000 times but each time with a new treatment group assignment (which is a permutation of the original treatment labels, i.e. take a 100% random sample of the original treatment variable without replacement) and a new trimming fraction appropriate to the current permutation.
9. Order the 10,000 permuted trimmed mean differences and count the number of those mean differences that exceed the observed trimmed mean difference calculated in Step 7 as n_1 .
10. Then the 1-sided empirical p-value of the original trimmed mean difference = $n_1/10000$.

The one-sided p-values will be presented for each rozanolixizumab dose compared to placebo.

The p-values from Stage 1 and Stage 2 will be combined in the same manner as the primary analysis. Specifically, the final one-sided p-value is $p = 1 - \Phi\left[\frac{1}{\sqrt{2}} \{\Phi^{-1}(1 - p_1) + \Phi^{-1}(1 - p_2)\}\right]$.

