8.3.5 Change from Baseline in PRO Physical Fatigue score

The PRO Physical Fatigue score is based on the MG symptoms PRO instrument items 19-33.

The same stage-wise MMRM model and analysis approach as specified in [Section 8.2.2](#) will be implemented to test for superiority.

The following analyses will be performed:

- Secondary: The same approach as specified in [Section 8.2.2](#) will be implemented.
- Sensitivity: The same approach as [Section 8.2.3.2](#) will be applied.
- Supplemental: The same approach as [Section 8.2.4.1](#) will be applied. The worst PRO Physical Fatigue score is 100.

- Additional: The same approach as [Section 8.2.5](#) will be applied.
- Exploratory: The same approach as [Section 8.2.6](#) will be applied.

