8.3.6 Change from Baseline in PRO Bulbar Symptoms score

The PRO Bulbar Symptoms score is based on the MG symptoms PRO instrument items 6-15.

The following analyses will be performed:

- Secondary: The same approach as specified in [Section 8.2.2](#) will be implemented.
- Sensitivity: The same approach as [Section 8.2.3.2](#) will be applied.
- Supplemental: The same approach as [Section 8.2.4.1](#) will be applied. The worst PRO Bulbar Symptoms score is 100.
- Additional: The same approach as [Section 8.2.5](#) will be applied.
- Exploratory: The same approach as [Section 8.2.6](#) will be applied.

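### On the 0-100 MG Symptoms PRO scales, the trimmed-mean analysis imputes a raw worst score but ranks on baseline-adjusted change, so high-baseline treatment failures need not rank worst and can escape trimming

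*SAP*

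**What the plan says.** SAP 8.2.4.1 sets out the trimmed-mean analysis for MG-ADL in ten steps, run separately in each stage. The relevant ones are:

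- **Step 3** defines the ranking variable: "Calculate the adjusted endpoint for each study participant as based on the raw CfB and coefficients calculated from the ANCOVA in Step 1". It is the raw change from baseline minus the fitted terms for baseline score, region and antibody status.
- **Step 4** deals with missing data and intercurrent events: "A worst score (i.e., 24) will be imputed for these study participants at Day 43". The stated reason is "in order to flag them as worse responders than any subject who completes".
- **Step 5** sets the trim fraction: "This will be the maximum of dropout and intercurrent event rate in each of the three treatment groups".
- **Step 6** orders the participants: "Sort each treatment group in ascending order by adjusted endpoint Day 43 MG-ADL score". Equal fractions are then cut from the bad end of each arm.
- **Step 7** summarises: "Calculate the mean adjusted CfB score of the trimmed sample for each treatment group".

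Sections 8.3.4 to 8.3.6 apply this unchanged to the three MG Symptoms PRO endpoints and replace only the worst score: "The worst PRO Physical Fatigue score is 100" and "The worst PRO Bulbar Symptoms score is 100", with the same value for Muscle Weakness Fatigability. Protocol 8.1.4.2 gives the range of these scales as 0 to 100, higher being worse. Under the composite strategy in SAP 8.1, every intercurrent event is to count as a treatment failure.

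**The concern.** The imputed value is on one scale (the Day 43 questionnaire score) and the ranking is on another (adjusted change). A participant who needed rescue and started near the top of the scale has little room to worsen, so imputing 100 gives only a small change. A completer who started lower and worsened substantially can then rank worse. That completer is trimmed, and the failure stays in the mean with an artificial value.

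Trimming handles treatment failure only if the failures are the observations removed. For the three PRO endpoints, which are the last three families in the testing hierarchy of SAP 4.6, this is the only composite-strategy analysis planned. What is at stake is whether it delivers that strategy.

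**Working it through.** **Inputs from the documents.** SAP 13.4 scores each PRO scale as (item sum / raw range) × (items / non-missing items) × 100. At the item maxima this is 60/60, 36/36 and 30/30, each × 100 = 100, which reproduces the stated worst score. For MG-ADL, 8 items × 3 = 24, as in step 4. Stage 1 has about 30 participants per arm (SAP 2.4).

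**The ranking variable.** Let B be baseline, Y the Day 43 score and b the baseline coefficient in the step 1 model of change. Omitting region and antibody terms:

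adjusted change = (Y − B) − bB = Y − βB, with β = 1 + b.

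A failure has Y = 100, so its value is 100 − βB_f. A completer ranks worse than that failure when

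Y_c − βB_c > 100 − βB_f, that is, β(B_f − B_c) > 100 − Y_c.

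The baseline adjustment gives back part of the ceiling effect. The dependence on baseline disappears only at β = 0.

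**Worked case.** A failure with baseline 90 against a completer going from 40 to 70:

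| β | Failure: 100 − 90β | Completer: 70 − 40β | Ranks worse |
|---|---|---|---|
| 0.5 | 55 | 50 | failure |
| 0.7 | 37 | 42 | completer |
| 1.0 | 10 | 30 | completer |

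The order reverses above β = 30/50 = 0.6.

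**Effect of one swap.** With 3 failures among 30 (10%) and no spare trimming places, 27 participants are kept. At β = 0.7, keeping the 37 instead of the 42 lowers that arm's mean by 5/27 = 0.19 points, towards benefit.

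**Frequency and size.** The documents give no means, SDs or failure rates for the PRO scales, so the following rests on assumptions: 30 per arm, baseline mean 40 to 60 (SD 20), β 0.6 to 1.0, residual SD 15 to 20, active effect −12. Steps 1 to 7 were simulated as written and compared with a version that ranks all failures last.

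| Failure rates (placebo/dose/dose) | Mean shift in treatment difference |
|---|---|
| 10/10/10% | 0 to 0.2 points |
| 20/10/10% | up to about 0.6 points, against the drug |
| 5/15/15% | up to about 0.13 points, in the drug's favour |

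With 10% failures in each arm, about 0.2% to 18% of failures escape trimming. The largest shift in a single simulated data set was about 3.5 points. Allowing baseline SD up to 25 and making failure likelier at high baseline raised the escape rate to as much as 25% and the largest single-data-set shift to about 5 points.

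The direction follows from step 5. The arm with the highest failure rate has no spare trimming places, so escapes concentrate there and lower that arm's mean.

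**Other scales.** With assumed baselines, the escape rate was 0.1% to 0.5% for MG-ADL, about 0.02% for QMG and 0.04% to 0.12% for MG-C.

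**The case against.** The strongest reply is that the intent is explicit and the wording can be read benignly. Step 4 follows the adjustment in step 3 and calls the imputation a flag, and step 6 refers loosely to a Day 43 score. If 100 were written straight into the adjusted variable, or the sort used the Day 43 score itself, failures would rank worst. That reading is possible but strained: step 3 defines the adjusted endpoint as an adjusted change, step 4 and Table 8-2 describe the imputed value as a questionnaire score, and step 7 averages adjusted change. Two programmers could differ, which is itself a reason to settle the sentence.

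Three further points stand and limit the concern.

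- A reader might compare raw changes, for instance a failure at baseline 80 (+20) with a completer going from 30 to 60 (+30), and conclude that the problem is common. The plan ranks on adjusted change. That pair reverses only when 100 − 80β < 60 − 30β, that is, above β = 40/50 = 0.8. At β = 0.7 the failure (44) still ranks worse than the completer (39).
- A reader might infer an inflated type I error. Steps 8 to 10 repeat the trimming for every relabelling on the same adjusted values, so the defect enters the permutation distribution as well and does not inflate the error rate under the null.
- High baselines are less plausible for Bulbar Symptoms, because the eligibility criteria exclude Grade 3 oropharyngeal or respiratory weakness and MGFA class IVb. The upper figures are more relevant to the two fatigue scales.

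**Conclusion.** The point holds in a limited form. As written, the procedure does not guarantee what step 4 says the imputation is for: on the 0-100 PRO scales, high-baseline failures need not rank worse than every completer. How often they fail to do so depends on the baseline distribution, β and the residual SD, none of which the documents give. The average effect on the treatment difference is small on a 100-point scale, although single data sets can shift by several points.

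The documents do not support reading this as a consistent bias towards the drug. The direction depends on which arm has more failures, and the larger shift found was against the drug. Nor do they support extending it to the trial's conclusions. These are supplementary analyses of secondary endpoints. The primary analysis and the hierarchy in SAP 4.6 rest on the mixed-model combination p-values, and a jump-to-reference sensitivity analysis is also planned. The correction is worth making because the rule defeats its own stated purpose and costs almost nothing to repair.

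**What to change.** Amend steps 4 and 6 of SAP 8.2.4.1 to state that, after covariate adjustment, all participants with missing Day 43 data or an intercurrent event rank below every completer regardless of baseline, for example by assigning them a value above the largest completer adjusted change in that stage. Apply this to every endpoint that uses the method (MG-ADL and 8.3.2 to 8.3.6), and reword step 6 so that the sort variable is unambiguous.

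No failure can then remain in the trimmed mean. If f is the largest failure rate and an arm of n participants has k failures, then f ≥ k/n, so f × n ≥ k. As k is a whole number, this holds even if the trim count is rounded down.

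The cost is one or two sentences in the SAP and one line of code, with no change to data collection or to the confirmatory analyses.

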2.4 Determination of sample size

As detailed in [Section 4.4](#), this study will consist of 2 stages, with a formal interim analysis at the end of Stage 1.

Based on historical data, the mean difference in adjusted changes from Baseline of MG-ADL at Day 43, between rozanolixizumab and placebo, is assumed to be 1.5 to 2.0 and the standard deviation is assumed to be 3.5 to 4. A difference of >1.5 could be judged to be clinically meaningful.

It is proposed that the interim analysis will be conducted when approximately 90 eligible study participants have been treated and are evaluable for the primary endpoint, i.e., approximately 30 study participants per dose group in Stage 1. If the study is not stopped for futility after Stage 1, the sample size will be increased, subject to a maximum cap, to provide an overall conditional power target of 90% based on the observed effect size in Stage 1. For each dose that is not futile, the comparison-wise conditional power will be calculated which is the probability of, given the observed data, to achieve a significant result for the completed trial if only the considered treatment is selected. If two doses are selected, then the conditional power associated with the higher treatment effect will be used to determine the stage 2 sample size. Conditional power will be calculated as described in formula 7.2 of Wassmer and Brannath (2016). Similarly, the stage 2 sample size required to achieve a target conditional power of 90% will be calculated using a formula derived from formula 7.4 of Wassmer and Brannath (2016) as follows:

$$\text{Second stage sample size per arm} = 2 * SD^2 * [\phi^{-1}(TP) + \phi^{-1}(1-CRP)]^2 / \Delta^2$$

Where,

SD = pooled standard deviation from the stage 1 statistical model using all dose groups

TP = target conditional power = 0.9

CRP = Conditional rejection probability at stage 1 for the dose group being considered

Delta = assumed true treatment effect for second stage data

If two doses are considered for stage 2 then the above formula will be applied with the conditional error divided by two, to account for multiplicity. Depending upon the selection of one, or two, of the doses after Stage 1, a further 60 to up to a maximum of 150 eligible study participants will be randomized in Stage 2 of the study. Thus, the total sample size of the study could range between 150 and 240 study participants if the study is not futile at Stage 1.

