The power of the study using the above adaptive design and expected sample sizes with a sample size cap of 80 per arm and various scenarios of true treatment effect and standard deviation were determined from a stimulation study using the statistical software ADDPLAN MC, the results of which are summarized in [Table 2-1](#).

The simulation results also indicate that across the various scenarios the average sample size for the study ranges between 169 and 203 study participants. The power for scenarios 5 to 7 and 12 to 14, that is, when the high dose has an effect compared to placebo of 2 points, are at least 80%, indicating that the sample size re-assessment process helps maintain reasonable power when only one dose has a clinically meaningful effect of 2 and the data variability is greater than anticipated (standard deviation[SD]=4).

The chances of stopping the study for futility i.e. both doses individually futile, when at least one dose has a clinically meaningful true effect of 2 or more versus placebo, is less than 3%.

These results support the strategy of entering 30 eligible study participants per dose group in Stage 1 and between 30 to 50 study participants per dose group in Stage 2. Note that ADDPLAN MC implements the sample size increase rule 'per arm' rather than 'per stage', so that if only one dose is selected for Stage 2, then the maximum sample size for this stage is 100, whereas if two

doses are selected than the maximum Stage 2 sample size is 150. Therefore, if an overall study sample size cap of 240 (i.e., 150 in Stage 2) were implemented, irrespective of whether one or two doses are selected, then we would expect power for each scenario to be slightly increased compared to those contained in [Table 2-1](#).

Table 2-1: Simulation results from ADDPLAN MC (x100,000 simulations per scenario) with a capped maximum sample size of 80 per arm using a Bonferroni intersection test

Scenario	Treatment Effect		Standard Deviation	Power	Interim			Average Sample Size
	Dose 1	Dose 2			Proportion Futility	Proportion Selecting Low Dose	Proportion Selecting High Dose	
1	0.0	0.0	3.5	0.020	0.335	0.474	0.474	169.0
2	1.0	1.0		0.400	0.049	0.781	0.782	203.3
3	1.0	1.5		0.632	0.023	0.657	0.914	199.1
4	1.5	1.5		0.750	0.011	0.838	0.841	199.8
5	1.0	2.0		0.864	0.008	0.474	0.975	186.4
6	1.5	2.0		0.892	0.004	0.697	0.942	191.7
7	2.0	2.0		0.943	0.002	0.859	0.860	189.9
8	0.0	0.0	4.0	0.020	0.335	0.467	0.463	168.1
9	1.0	1.0		0.315	0.066	0.734	0.733	199.9

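### SAP 8.2.4.1 shuffles all three arms to test each dose against placebo, so one dose's trimmed-mean p-value depends on the other dose, with bias possible in either direction

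*SAP*

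**What the plan says.** SAP 8.2.4.1 (Supplementary Analysis #1) counts a participant with missing Day 43 data or an intercurrent event as a failure and assigns the worst score. It then trims an equal fraction from each arm and compares trimmed means by permutation. Four features matter here:

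- Trim fraction (step 5): "This will be the maximum of dropout and intercurrent event rate in each of the three treatment groups".
- Permutation (step 8): steps 5 to 7 are repeated 10,000 times on relabelled data; the instruction is to "take a 100% random sample of the original treatment variable without replacement", with "a new trimming fraction appropriate to the current permutation".
- Result: "The one-sided p-values will be presented for each rozanolixizumab dose compared to placebo".
- Stages: "The trimmed mean approach will be applied for each stage separately as follows". The two stage p-values are then combined by the equal-weight inverse normal method.

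Nothing restricts the shuffle to the two arms being compared. SAP 8.3.2 to 8.3.6 apply the same procedure to MG-C, QMG and the three MG Symptoms PRO scores.

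**The concern.** A permutation test is exact when the permuted labels are exchangeable under the hypothesis tested. The hypothesis that one dose equals placebo says nothing about the other dose. Shuffling all three arms puts the other dose's scores and failures into both the permuted placebo sample and the permuted tested-dose sample. It also makes the permuted trim fraction behave differently from the observed one. The reference distribution is then right only under the global null.

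Unequal arms are a realistic prospect. SAP Table 2-1 itself plans for unequal effects, such as 1.0 and 2.0. The composite strategy counts both rescue and permanent discontinuation for TEAEs as failures, and protocol 4.3 reports more frequent and more severe headache on active drug. The stake is the credibility of the only worst-score analysis of the continuous primary endpoint, whose purpose is to show what happens when failures are counted against treatment.

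**Working it through.** **Inputs from the SAP.** Section 2.4: "approximately 30 study participants per dose group in Stage 1", "between 30 to 50 study participants per dose group in Stage 2", effect 1.5 to 2.0 points, SD 3.5 to 4. Section 4.6: two-sided 0.025 per dose for the primary endpoint, that is one-sided 0.0125, used here only as a reference level. Section 8.2.4.1 gives no planning failure rates, only an illustration ("if the rate of dropout/IE in the three groups is 10, 15 and 20" per cent). Rates from 0 to 30% per arm are therefore assumptions.

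**The plan's own figures.** The trim illustration reproduces: max(10, 15, 20) = 20%. The SAP gives no size or power for the trimmed-mean test. As a check on the design inputs, a simulation of the two-stage design gives power 0.949 for Table 2-1 scenario 7, against the stated 0.943.

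**Effect of the other dose's efficacy (equal failures, ignoring trimming).** Let a be the tested dose's effect, b the other dose's, and s the SD. The variance of the shuffled pool is:

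- three arms: s² + Var(0, a, b) = s² + 2(a² + b² − ab)/9
- two arms: s² + a²/4

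For a > 0 the three-arm null is wider only if 8b² − 8ab − a² > 0. That means b/a > (8 + √96)/16 = 1.11, or b in the opposite direction (b/a < −0.11). With s² = 12.25, a pairwise p of 0.0125 (z = 2.241) is rescaled by √(two-arm/three-arm variance):

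| tested, other effect | three-arm variance | two-arm variance | three-arm p |
|---|---|---|---|
| 0, 2 | 13.139 | 12.250 | 0.0152 |
| 1, 2 | 12.917 | 12.500 | 0.0137 |
| 2, 2 | 13.139 | 13.250 | 0.0122 |
| 2, 1 | 12.917 | 13.250 | 0.0116 |

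The shift is small and changes sign.

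**Effect of unequal failures (simulation).** One stage, 30 per arm, SD 3.5, normal adjusted scores, failures independent of score. Rates are placebo/tested/other; effects are points of improvement, tested/other. Size is at one-sided 0.025, power at one-sided 0.0125. Most rows use 4,000 data sets with 1,000 permutations each; the 5/5/20% rows come from 5,000 with 250. Where several values are shown, they are separate runs.

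| failures % | effects | measure | three-arm shuffle | pairwise shuffle |
|---|---|---|---|---|
| 5/5/20 | 2/2 | power | 0.283, 0.289 | 0.363, 0.370 |
| 5/5/20 | 0/2 | size | 0.015 | 0.022 |
| 5/5/30 | 2/2 | power | 0.279 | 0.402 |
| 5/5/30 | 0/0 | size | 0.015 | 0.030 |
| 20/20/5 | 0/0 | size | 0.032, 0.036, 0.038 | 0.024, 0.026, 0.030 |
| 20/20/5 | 0/2 | size | 0.031 | 0.027 |
| 15/5/5 | 2/2 | power | 0.591 | 0.573 |
| 10/15/20 | 2/2 | power | 0.193 | 0.201 |
| 10/10/10 | 2/2 | power | 0.317 | 0.318 |

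The Monte Carlo standard error of a size of 0.025 from 4,000 data sets is √(0.025 × 0.975/4000) = 0.0025. The 0.036 from that run is thus about four standard errors above nominal.

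**Why the sign changes.** The comparator for the SDs here is a pairwise shuffle that keeps the third arm's rate in the trim maximum. At 5/5/30% with no effects, the observed data lose on average 9.05 participants per arm to trimming but the permuted data only 5.61. The SD of the permuted differences is 1.136, against 1.008 for the comparator: too wide, so p is too large. At 20/20/5% the SDs are 1.16 and 1.24: too narrow, so p is too small.

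**Check of the fix.** Across the null scenarios of the 4,000-data-set run, the pairwise shuffle had size 0.019 to 0.030 with the trim maximum over two arms, and 0.020 to 0.028 with the third arm's observed rate held fixed in the maximum. The three-arm shuffle ranged from 0.011 to 0.036.

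**The case against.** The analysis is supplementary. No alpha is assigned to it; the primary test is the stage-wise MMRM (SAP 8.2.2), and the gatekeeping in SAP 4.6 takes its p-values from that approach. If one dose is dropped, Stage 2 has two arms and the problem vanishes there. With the SAP's illustrative 10/15/20% rates, the power difference is under one point. All of this stands, and it limits the consequence. It does not make the pairwise p-value valid: Stage 1 always has three arms and carries half the squared weight in the combination.

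A reader might infer that the p-value is always too large and that the method simply loses power. The documents do not support that, because they fix neither the failure rates nor the relative effects. When the other dose has fewer failures than the compared pair, the p-value can be too small. Nor is the other dose's efficacy the main driver: with both effects at 2 and equal failures, the pairwise p of 0.0125 becomes 0.0122. The loss at 5/5/20% comes from the assumed failure imbalance.

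**Conclusion.** The point holds as a defect in a stated rule: in a three-arm stage, the permutation test in SAP 8.2.4.1 is not valid for the pairwise hypothesis it reports on. The size of the error depends on how far the other dose's failure rate departs from that of the compared pair: about 8 points of power lost at 5/5/20%, inflation of a 0.025 test to about 0.032-0.038 at 20/20/5%, and practically nothing with equal failures and similar effects. Inflation is the more serious direction. These figures rest on assumed failure rates, one stage of 30 per arm, SD 3.5, normal scores, and failure independent of score; the combined two-stage error was not simulated. The reach is the composite-strategy supplementary analyses of MG-ADL and the five continuous secondary endpoints. Confirmatory conclusions are untouched. The change is worth making because it is cheap and these analyses are meant to support robustness.

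**What to change.** Amend steps 5 and 8 of SAP 8.2.4.1. Within each stage and for each dose, permute labels only among participants randomised to that dose or to placebo, then repeat for the second dose. State the trim rule explicitly, for the observed and the permuted data alike: either the maximum failure rate over those two arms, or that maximum with the third arm's observed rate kept in as a fixed value. Either choice gave near-nominal size. Permutation within antibody stratum is not needed: the scores are already covariate-adjusted, and SAP 3.9 replaces the single stratification factor with two binary variables, so the stratum would itself need defining. The cross-references in SAP 8.3.2 to 8.3.6 carry the change to the secondary endpoints. The cost is a small code change and one extra permutation run per three-arm stage, with no effect on data collection or on the primary test.

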3 DATA ANALYSIS CONSIDERATIONS

3.1 General presentation of summaries and analyses

Statistical analysis and generation of tables, figures, participant data listings, and statistical output will be performed using SAS® Version 9.3 or higher. All tables and listings will use Courier New font size 9.

Descriptive statistics will be displayed to provide an overview of the study results. For continuous variables, descriptive statistics will include number of participants with available measurements (n), mean, SD, median, minimum, and maximum.

For categorical variables, the number and percentage of participants in each category will be presented. Unless otherwise noted, the denominator for percentages will be based on the number of participants included in the respective analysis set. Participants with missing data can generally be accounted for using the following approaches:

- For summaries of demographics and Baseline characteristics: summarize percentages based on all participants in the analysis set and include a “Missing” category (corresponding to participants with missing data for the variable being summarized) as the last row in the list of categories being summarized.
- For summaries of efficacy and safety variables, unless otherwise specified: summarize percentages based only on those participants with observed data for the variable being summarized. As the denominator may be different from the number of participants in the analysis set being considered, the denominator should be displayed in the table. The general format for displaying this will be “n/Nsub (%)”

Unless otherwise noted, all percentages will be displayed to one decimal place. No percentage will be displayed for zero counts, and no decimal will be presented when the percentage is 100%.

For the purpose of the tabulations the lower and upper confidence limits for the percentages will be truncated at 0 and 100% respectively.

Statistical tests of efficacy variables will be presented as p-values rounded to three decimal places. P-values less than 0.001 will be presented as “<0.001” and p-values greater than 0.999 will be presented as “>0.999”. Statistical comparisons will be two-sided and will be performed at the 0.05 level of significance unless specified otherwise. The significance levels used as part of the multiple testing procedure are detailed in [Section 4.6](#).

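### Trimmed-mean analysis: a stage permutation p-value can be exactly 0, and it then forces the combined p to 0 for any other-stage p below 1

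*SAP*

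**What the plan says.** SAP 8.2.4.1 runs the trimmed-mean procedure separately in each stage. Step 7 asks for "the difference between trimmed means of each rozanolixizumab group and placebo" without giving the order of subtraction. Step 8 generates 10,000 relabelled data sets. Step 9 says to "count the number of those mean differences that exceed the observed trimmed mean difference calculated in Step 7", and calls that count n1. Step 10 reads "Then the 1-sided empirical p-value of the original trimmed mean difference" and sets it equal to n1/10000. The text then states: "The p-values from Stage 1 and Stage 2 will be combined in the same manner as the primary analysis". The formula given is the equally weighted inverse normal combination.

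No step adds the observed labelling to the count, sets a minimum, or says what to do when n1 is 0 or 10,000. SAP 8.3.2 to 8.3.6 apply the same procedure to the five continuous secondary endpoints. SAP 3.1 has a display rule ("P-values less than 0.001 will be presented as" a less-than sign with 0.001), but it governs only how a value is printed.

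**The concern.** The observed labelling is one of the possible permutations, so the true permutation p-value cannot be 0. A zero arises only because 10,000 random relabellings are drawn and the observed one is left out of the count. On its own that would be a rounding matter. Here the zero is passed to the inverse normal function, which returns infinity, and the stages are added afterwards. The design gives each stage a weight of 1/√2. After a zero, the other stage has no influence at all.

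At stake is the planned composite-strategy check of the primary result and its five repeats. A second stage that showed nothing, or leaned the wrong way, would be hidden behind a combined p printed as below 0.001. Handling of an infinite or undefined statistic would be left to the programmer.

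**Working it through.** The SAP gives no numerical result for this analysis, so there is no figure to reproduce. Its formulas can be evaluated directly.

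**Inputs.** B = 10,000 permutations, strict counting, stage p = n1/B (8.2.4.1, steps 8 to 10); weights 1/√2 (8.2.2); display rule (3.1).

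**Formula.** With z_i = Φ⁻¹(1 − p_i), combined p = 1 − Φ[(z₁ + z₂)/√2]. Check: p₁ = p₂ = 0.5 returns 0.5.

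**As written.** n1 = 0 gives p₁ = 0 and z₁ = +∞. The sum is +∞ for every finite z₂, so combined p = 0. If p₂ = 1, then z₂ = −∞ and the sum is undefined.

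**Corrected.** With p = (n1+1)/(B+1), the smallest stage p is 1/10001 = 0.00009999, so z₁ = 3.719. Example with p₂ = 0.90: z₂ = −1.282, (3.719 − 1.282)/1.414 = 1.72, combined p = 0.042.

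| Other-stage p | Combined p as written | Combined p corrected |
|---|---|---|
| 0.025 | 0 | 0.00003 |
| 0.30 | 0 | 0.0013 |
| 0.50 | 0 | 0.0043 |
| 0.80 | 0 | 0.021 |
| 0.90 | 0 | 0.042 |
| 0.99 | 0 | 0.162 |
| 1 | undefined | 1 |

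**Where it matters.** For a combined one-sided threshold a, the corrected value exceeds a once z₂ < √2·z_a − 3.719.
- a = 0.001 (printed value changes): 1.414 × 3.090 − 3.719 = 0.651, so p₂ > 0.257.
- a = 0.0125: 1.414 × 2.241 − 3.719 = −0.549, so p₂ > 0.71.
- a = 0.025: 1.414 × 1.960 − 3.719 = −0.947, so p₂ > 0.83.

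**How often a zero occurs: approximation.** SAP 2.4 assumes that the mean difference "between rozanolixizumab and placebo, is assumed to be 1.5 to 2.0" points, with SD 3.5 to 4, 30 per arm in Stage 1 and "between 30 to 50 study participants per dose group in Stage 2". With a normal stage statistic of mean δ/(SD·√(2/n)) and no trimming, P(n1 = 0) = E[(1 − p)^10000]. Per stage this is 1.0% (δ 1.5, SD 4) to 5.8% (δ 2, SD 3.5) at 30 per arm, and 2.9% to 17.1% at 50 per arm.

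**How often a zero occurs: simulation of steps 4 to 10.** The trimming fraction was recomputed in every permutation. There were 1,000 trials in each of 24 settings:
- Effects 1.5/1.5, 1.0/2.0 and 2.0/2.0, with SD 3.5 or 4.
- Failure rates are assumed, because the SAP gives none: 5% in all arms, 10% in all arms, or step 5's illustration ("if the rate of dropout/IE in the three groups is 10, 15 and 20" per cent) with placebo highest or lowest.
- Doses carried forward by the 1-point rule of SAP 4.4.1; Stage 2 fixed at 30 or at 50 per arm; no covariates.

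| | Stage 2 at 30/arm | Stage 2 at 50/arm |
|---|---|---|
| At least one zero | 3.0% (0.1–9.6% by setting) | 5.6% (0.3–17.8%) |
| Printed combined p changed in a zero case | 0.38% | 0.60% |

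Across both sizes there were 77,070 dose comparisons and 3,321 zero cases. In 380 of those (380/3,321 = 11%) the printed value changed; the corrected value had median 0.0024 and maximum 0.085. Significance was lost in 11 comparisons at one-sided 0.025 and in 26 at 0.0125. No zero was paired with a p of 1.

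**Direction of subtraction.** Higher MG-ADL is worse (SAP 13.3), so benefit is a negative change. In three simulated stages with a true 2-point benefit, rozanolixizumab minus placebo gave n1 of 9,571 to 9,879 and placebo minus rozanolixizumab gave 121 to 429. The intended tail can be inferred: SAP 2.4 writes benefit as positive, and SAP 4.4.1 reads a one-sided p above 0.5 as the wrong direction. This is a clarification only.

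**The case against.** The strongest case against is that this hardly matters.

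- **Impact.** The analysis is supplementary and outside the tests in SAP 4.6. Under the null, one-sided size at 0.025 is about 0.0251 as written and 0.0249 corrected. About 89% of zero cases print the same either way. The SAP also presents one-sided p-values for each dose; if these are shown by stage, a weak stage would be visible. All this stands and limits the weight of the point. It does not make a combined p of 0 correct when the right value is 0.0043.
- **The correction disturbs other results.** Of the 73,749 comparisons without a zero, it changed the printed combined p in 9.6% and moved 61 across 0.025, against 11 among the zero cases. A floor applied only at n1 = 0 would remove the infinity and leave the rest alone. That is a workable minimum. The other shifts are slight, however, and they come from counting the observed labelling, which is what makes the result a proper permutation p-value.
- **The upper end remains.** n1 = 10,000 still gives p = 1 and a combined p of 1. That is conservative, and p = 1 is a possible permutation value, whereas 0 is not.
- **The frequencies depend on chosen settings.** Only 6 of the 14 scenarios in Table 2-1 were simulated, leaving out the smaller effects, where zeros are rarer. The percentages are therefore illustrative. The algebra does not depend on them.

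**Conclusion.** The concern holds. Step 10 with the stated combination formula gives a combined p of exactly 0 whenever one stage has n1 = 0 and the other has p below 1, and no value when the other has p = 1. This follows from the SAP's formulas alone.

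The error is visible in print only if the other stage's p exceeds about 0.257. It alters significance only if that p exceeds about 0.71 (one-sided 0.0125) or 0.83 (one-sided 0.025). The simulated frequencies rest on the SAP's effect sizes and SDs, assumed failure rates, fixed Stage 2 sizes and no covariate adjustment. The confirmatory conclusions are not touched. The rule should still be corrected, because it gives a wrong number and is used for six endpoints.

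**What to change.** In SAP 8.2.4.1:

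- Step 10: set the one-sided p to (n1+1)/(10000+1).
- Step 9: count permuted differences greater than or equal to the observed one. This goes with the +1 rule; no ties occurred in the simulation.
- Step 7: state that the difference is placebo minus rozanolixizumab, so that positive values favour rozanolixizumab. This agrees with SAP 2.4 and Table 2-1 and keeps step 9's upper tail.

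Because 8.3.2 to 8.3.6 refer back to this section, the change carries over. The cost is three short text edits and one line of code. The smallest reportable stage p becomes 0.0001, and other p-values rise slightly.
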